#### Efficiency and productivity metrics such as tracking the effectiveness and outcomes of recruitment strategies employed

We have the data to determine the enrollment ratios.

- Numerator: we have developed tracking databases for the RAs to record the number of approached patients per month. They further document the reason for ineligibility among subjects. For eligible subjects, the RAs further document which patients consent or decline to participate, and for those that decline, the reasons for not participating.
- Denominator: On a periodic basis, administrators at the LAC-DHS run reports for the SUSTAIN team that show the number of patients hospitalized at each site per month.

Using our tracking databases and the LAC-DHS reports, we can calculate the proportion of hospitalized stroke patients approached by our research team and the proportion of eligible stroke patients who consent to participate in the study. This will allow us to discern when and where and why study enrollment rates are lower than expected.

These enrollment statistics will be shared among the research team and the Task Force. If rates of participating are lower than expected at a site, we will investigate the reasons for doing so and develop strategies for overcoming barriers. This feedback loop has been critical for developing our successfully recruitment strategy in SUSTAIN.

## 5 STUDY INTERVENTIONS

### 5.1 Interventions, Administration, and Duration

The intervention team consists of the following:

- Care Managers
- Community Health Workers
- Research Assistants

The intervention is:

- Care by CM
- Medical algorithms
- Report cards

Community Health worker home visits and community self management classes, supported by mobile technology.

### 5.2 Handling of Study Interventions

Not applicable

### 5.3 Concomitant Interventions

#### 5.3.1 *Required Interventions*

Not applicable

#### 5.3.2 *Prohibited Interventions*

Not applicable

#### 5.3.3 Precautionary Interventions

Not applicable

### 5.4 Adherence Assessment

For subjects randomized to the intervention arm, we will document the number of encounters between subjects and the intervention team. This will include the number of face-to-face visits, number of telephone calls, number of classes attended, and the number of home visits.

## **6 CLINICAL AND LABORATORY EVALUATIONS**

The Schedule of Evaluations in section 6.1 indicates all study evaluations. An 'X' in a cell indicates that a particular evaluation is to be performed at a particular study visit.

The definitions for the Schedule of Evaluations are included in section 6.2 where evaluations are defined, timelines are provide, special considerations or instructions for evaluations are included.

### 6.1 Schedule of Evaluations

Evaluation	Screening/ Baseline	On-Intervention			Off-Intervention		
		3 months	8 months	12 months	18 months	24 months	30 months
Informed Consent	X						
Physical Exam: Blood Pressure (BP), Body Mass Index (BMI), Waist-Hip Ratio, Waist-to-Height Ratio, NIH Stroke Severity Scale, Modified Rankin Scale	X	X	X	X			
Finger Stick LDL (Triglyceride level, HDL cholesterol level, Hemoglobin A1c, C-reactive protein (CRP))	X	X	X	X			
Full In-Person Questionnaire	X	X		X			
Brief Telephone Questionnaire			X				
Telephone Surveillance (vascular events/death)					X	X	X

## **6.2 Timing of Evaluations**

### **6.2.1 *Pre-Randomization Evaluations***

\*Please note: All evaluations occur prior to the subject receiving any study interventions.

#### Screening, Entry Surveys, and Randomization

Screening for inclusion/exclusion criteria, baseline (entry surveys), and randomization occur in the same face-to-face encounter.

### **6.2.2 *On-Study/On-Intervention Evaluations***

See Section 6.1 for the schedule of evaluations occurring after randomization while the subject is on-study. The allowable window for evaluations during the on-intervention period is one month around each timepoint.

### **6.2.3 *Intervention Discontinuation Evaluations***

If patients wish to withdrawal from the study prematurely, we will attempt to administer the final outcome measurement survey. Additionally, the reason for discontinuation will be recorded.

Retention of subjects will be enhanced by collecting multiple phone numbers and addresses for each subject and multiple phone numbers for a close friend and family member.

### **6.2.4 *On Study/Off-Intervention Evaluations***

The evaluation schedule remains the same while the subject is “off intervention/on study” for SUCCEED (see Section 6.1).

### **6.2.5 *Final On-Study Evaluations***

The schedule of activities during the final 12 month measurement time point is the same as the baseline and 3 month time points, with the difference being that there is no need to conduct the randomization procedures other than the baseline time points.

After the study is completed, we will call the subjects every 6 months for up to 30 months after randomization to conduct surveillance of vascular events and ascertainment of mortality.

### **6.2.6 *Off-Study Requirements***

Once the subject has completed the protocol-specified period on study intervention, they will be follow-up with every 6 months for up to 18 months for the occurrence of vascular events and death. Refer to Section 6.1.

### **6.2.7 *Pregnancy***

Women who become pregnant while on-study, will be instructed to continue their normal care. No additional evaluations are needed.

## **6.3 Special Instructions and Definitions of Evaluations**

### **6.3.1 *Informed Consent***

The patient education and informed consent process has been detailed in Section 4.3.3. Further, plans review of consent document in case changes may be required and how documentation of signed consent will be maintained by the study are outlined in that section.

*A model informed consent form should has been included as Appendix. When developing the consent form, consider including language allowing for the retention of study data and specimens beyond the*

*close of this study, for sharing the de-identified data and specimens with other researchers, and for using the specimens for purposes beyond the scope of this study.*

#### 6.3.2 *Documentation of [specify the Disease/Disorder under study]*

We will review administrative databases to determine if the patient has suffered a stroke, myocardial infarction, and death during the study period.

#### 6.3.3 *Medical History*

Self report in a survey. We will review administrative databases to determine if the patient has suffered a stroke, myocardial infarction, and death during the study period.

#### 6.3.4 *Treatment History*

Self report in a survey

#### 6.3.5 *Concomitant Treatments*

Not applicable

#### 6.3.6 *Study Intervention Modifications*

Not applicable

#### 6.3.7 *Clinical Assessments*

Because NINDS strongly encourages investigators to make use of the NINDS Common Data Elements in developing the CRFs (see <http://www.commondataelements.ninds.nih.gov/>), the study team will rely on those materials in the development of CRFs for SUCCEED.

**Blood Pressure (BP):** Participants are seated quietly for 5 minutes before Blood Pressure (BP) reading are initiated. Staff are trained to ensure that the proper cutoff size is used and that the participant's arm is resting on a flat surface, with the BP cuff at heart level. Two sequential readings will be taken using the OMRON 90XL with 5 minute intervals between each reading. If the first two readings differ by more than 5mmHg, then an additional two readings are taken and recorded electronically using a laptop based data entry system developed through Core A. Average BP is calculated by the data collection system.

**NIHSS and disability scales:** Each RA will obtain certification to perform the National Institute of Health Stroke Scale (NIHSS) and the modified Rankin scale prior to the start of the study. These are measures of stroke severity and disability. Certification is obtained by completing the following courses and taking a test by scoring an online video of a patient.

<http://nihss-english.trainingcampus.net/uas/modules/trees/windex.aspx> and

<http://rankin-english.trainingcampus.net/uas/modules/trees/windex.aspx?res>.

In addition, the RA will be observed by the site PI for at least the first two study participants. Each RA will be re-observed examining a study participant 2 months later, then 4 months later.

#### 6.3.8 *Laboratory Evaluations*

**LDL Cholesterol:** Point-of-service CardioChek meters will be used to collect information on LDL cholesterol. The meters require only a small capillary blood sample (from a fingerprick). After cleaning the end of one finger with an alcohol wipe, a small lancet is used to prick the participant's finger. The first blood spot is wiped off with gauze and the next blood spot is dropped into a special cartridge which is then simply inserted into the CardioCHEK meter for the calculation of LDL cholesterol. Staff will record results electronically using the laptop-based data entry system.

**Glycosylated Hemoglobin (HgA1c) and C-Reactive Protein (CRP):** We will use dried blood spots (DBS) to obtain assays for these two parameters. Whatman 903 Protein Saver filter paper is used for DBS collection; this paper is commercially available as small cards. Participants should be well hydrated as this facilitates collection of adequate DBS. Staff are trained to ask about hydration and to provide some water if participant hasn't had much to drink recently. Participants are asked to wash their hands with very warm water, to remove lotions, and to aid blood flow. To further aid in blood flow to the hand, participants can be asked to wrap their hand in a heating pad or two hold a heat pack and/or to hang their arm down and shake their hand downward/ Similar to the CardioChek protocol, the end of one finger is then cleaned with an alcohol wipe, a small lancet is used to prick the middle or ring finger on the fleshy side. The first blood spot is wiped off with gauze. The following blood spot is allowed to "pool" on the finger and then to drop onto the collection card. (Whatman cards have circles printed on the card so blood spots can be dropped to fill-in each circle) Cards will be labeled with each subject's study ID, along with information on date and time of collection. Once blood spots have been collected, cards are placed as "drying boxes" as they require air for at least 2 hours. With cards individually "housed" in separate boxes, staff can stack boxes of cards over the course of a day as they collect samples from participants. Once cards have dried at least 2 hours, they are to be placed in a storage envelope with a dessicant packet (all supplies provided through Core C) and then frozen. Samples collected for Project 1 at hospital settings will be stored in local freezers and transported weekly to Core C freezers on the UCLA campus.

6.3.9 *Pharmacokinetic Studies*  
Not applicable

6.3.10 *Other Laboratory Studies*  
Not applicable

6.3.11 *Additional Evaluations*  
Not applicable

6.3.12 *Questionnaires*

Full in person Questionnaires:

Demographics, Stroke knowledge/attitudes, Medication adherence (simony scale), Competing needs, Access to care, Chaos questions (Outreach questionnaire), Perception of Neurological care (CHAHPS), Patient Health Questionnaire (PHQ2), Social support items, Medical Utilization items (including hospital and physicians visits and other medical services), RAND SF-6D

Brief Telephone Questionnaire:

Medication adherence (simony scale), Medical Utilization items (including hospital and physicians visits and other medical services)

6.3.13 *Adherence Assessments*

For subjects randomized to the intervention arm, we will document the number of encounters between subjects and the intervention team. This will include the number of face-to-face visits, number of telephone calls, number of classes attended, and the number of home visits.

## 7 MANAGEMENT OF ADVERSE EXPERIENCES

- Elder Abuse: Under California law, all healthcare employees are mandated to report elder abuse. If abuse is suspected during your encounter with the patient, the site PI will be contacted.
- Elevated Blood Pressure: If the subject experiences elevated blood pressure that meets the following criteria, the following steps should be taken:
  - If  $\geq 140$  – verbally inform the subject that their BP is at least 140 and give a card to the subject with the reading.
  - If  $\geq 180$  – inform the subject that they must see their doctor immediately. If the subject does not have a primary doctor, the patient must go to the emergency room.
- Suicide: Although the subject will not be asked specific questions regarding suicidality, if the subject expresses suicidal ideation or states they are thinking about harming themselves or have recently attempted to do so, the site PI will be contacted.

**8 CRITERIA FOR INTERVENTION DISCONTINUATION**

If a patient has optimal control of all risk factors, the criteria for discontinuing intervention are met, but that participant will still remain a part of the study.

## 9 STATISTICAL CONSIDERATIONS

### 9.1 General Design Issues

The primary and secondary hypotheses is that subjects randomized to the intervention arm will have better control of risk factors and higher rates of adoption of healthy lifestyle habits compared to the control arm.

All outcomes will be collected by a blinded RA. Vascular events will be collected by patient self-report and will not require an adjudication committee.

The design is a RCT, 1:1 allocation to control and intervention arms. There is no crossover.

Randomization is stratified by site (4), language (3: English, Spanish, other), and type of stroke (2: ischemic/TIA, hemorrhagic). There are 24 strata.

Intervention on period is up to 12 months for persons. It may be discontinued if subjects optimally control risk factors.

After the 12 month study period, subjects will be monitored by telephone for the presence of vascular events and mortality. There is no face-to-face contact, and thus, no collection of SBP, the primary endpoint. This surveillance is to better determine the impact of the intervention in the first 12 months after randomization.

### 9.2 Outcomes

#### 9.2.1 *Primary outcome*

Refer to **Table 1** provided below.

#### 9.2.2 *Secondary outcomes*

Refer to **Table 1** provided below.

**Table 1.** Primary & Secondary Outcomes

Primary Outcome
Blood Pressure (change in blood pressure, as well as proportion of patients with BP under 120/80)
Secondary Outcomes
Risk of recurrent stroke, future cardiovascular event
Lipid profile: LDL cholesterol level, Triglyceride level, HDL cholesterol level
Hemoglobin A1c
C-reactive protein (CRP)
Adiposity: Body mass index (BMI), waist circumference, Waist-hip ratio, Waist-to-Height Ratio
Healthy Lifestyle Behaviors & Factors: Physical Activity, Diet, Smoking, Alcohol Use
Death

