### Objectives

[figure not shown]
The primary objectives of this study are as follows:

- (1) To develop a *community-centered component* of a Chronic Care Model-based secondary stroke prevention intervention.
- (2) To test the impact of a sustainable Chronic Care Model-based intervention on control of systolic blood pressure (primary outcome), composite stroke risk, and each individual stroke risk factor (secondary outcomes), among 500 adults (over 90% minority) recruited “early” - during or shortly after hospitalization for an ischemic or hemorrhagic stroke or TIA - at one of the four Los Angeles County safety net medical centers.
- (3) To conduct a cost analysis of SUCCEED from the perspective of the Los Angeles County Department of Health Services, using intervention costs, cost equivalents of associated utilization of county system resources, and cost equivalents of observed and projected vascular events.

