### Figure 1. SUCCEED Study Design

We designate systolic blood pressure as the primary outcome for the purpose of sample size calculations. We will assess multiple relevant outcomes including all risk factors and a composite index, cost, quality of life, adverse consequences, moderators, mediators, and a range of metrics of intervention program implementation and participation.

Table 1 below shows the primary and secondary outcomes for SUCCEED.

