**Table 1. Primary & Secondary Outcomes**

Primary Outcome
Blood Pressure
Secondary Outcomes
Risk of recurrent stroke, future cardiovascular event
Lipid profile: LDL cholesterol level, Triglyceride level, HDL cholesterol level
Hemoglobin A1c
C-reactive protein (CRP)
Adiposity: Body mass index (BMI), waist circumference, Waist-hip ratio, Waist-to-Height Ratio
Healthy Lifestyle Behaviors & Factors: Physical Activity, Diet, Smoking, Alcohol Use
Death

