**Primary Objective #2:** To test the impact of a sustainable Chronic Care Model-based intervention on control of systolic blood pressure (primary outcome), composite stroke risk, and each individual stroke risk factor (secondary outcomes), among 500 adults (over 90% minority) recruited “early” - during or shortly after hospitalization for an ischemic or hemorrhagic stroke or TIA - at one of the four Los Angeles County safety net medical centers. We will conduct a randomized trial of this intervention that includes the new, community-centered component developed in aim #1, and a “re-engineered” healthcare delivery system with nurse practitioners or physician assistants as care managers, distribution of home blood pressure monitors, group clinics, and a care management software system tailored to secondary stroke prevention and interfaced with the mobile health platform used by the CHWs, relative to usual care. We will include non-English speaking individuals from Hispanic, Chinese, and Korean racial and ethnic groups, and a broad range of stroke severity. We will analyze potential moderators (age, gender, stroke type and severity, education, country of birth/primary language, diabetes comorbidity, care team composition) to understand robustness of intervention impacts across levels of individual and health system characteristics. We will conduct a formative evaluation to continuously improve implementation, and will measure and analyze extent of intervention implementation, as it is delivered for up to 12 months after stroke or TIA through transition of patients into primary care. We will analyze potential mediators (life chaos, competing needs, medication adherence, knowledge of stroke risk factors, participation in self-management programs, social isolation, depression, health literacy, engagement with healthcare provider team, attitudes/health beliefs, self-efficacy, readiness to change, perceived risk, and perceptions of quality of interactions with provider) of the intervention’s impact, using both qualitative and quantitative methods.

*Hypothesis: Patients randomized to the SUCCEED intervention will achieve 8mm greater reduction in systolic blood pressure reduction and lower stroke risk scores at 1 year versus those randomized to usual care.*

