### 4.2 Exclusion Criteria

4.2.1 *List any clinical contradictions. Specify grades of signs/symptoms*

Persons with language (aphasia) or cognitive difficulties are ineligible if they cannot communicate that they understand the study during the informed consent process.

4.2.2 *Clinical/laboratory indicators of current status, obtained within XX prior to randomization. List the specific tests to be performed and the narrowest acceptable range of laboratory values for exclusion, consistent for safety.*

Systolic Blood pressure > 120 mmHg

4.2.3 *Specify any exclusion related to pregnancy, lactation, or plans to become pregnant. Specify methods for assessing current status and willingness to use contraception, if applicable.*

Not applicable

4.2.4 *Use of excluded drugs, devices, etc. within XX days prior to entry*

Not applicable

4.2.5 *For drug studies: Allergy/sensitivity to study drugs or their formulations*  
Not applicable

4.2.6 *Specify any clinical (life expectancy, co-existing disease), demographic (age) or other characteristics that precludes appropriate diagnosis, treatment, or follow-up in the trial*

Young patients are excluded because the mechanism for their strokes is frequently not due to atherosclerosis (e.g. arterial dissections, congenital coagulation defects, etc), so the interventions in this proposal may not be as applicable to them. We will also exclude persons who already meet the primary outcome of SBP <120 mm Hg. We will not be able to translate written materials in languages other than English, Spanish, Korean, and Chinese. Patients who do not speak any of those languages will be excluded.

4.2.7 *Active drug or alcohol use or dependence that, in the opinion of the site investigator, would interfere with adherence to the study requirements.*

If the participant exhibited active drug or alcohol use or dependence that, in the opinion of the site investigator would interfere with adherence to study requirements, that participant would be excluded from the study.

4.2.8 *Serious illness (requiring systemic treatment and/or hospitalization) until subject either completes therapy or is clinically stable on therapy, in the opinion of the site investigator, for at least XX prior to the study. (List specific illnesses and acceptable time)*

Not applicable, hospitalized patients are being enrolled in the study.

4.2.9 *Inability or unwillingness of subject to give written consent.*

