### 9.3 Sample Size and Accrual

#### **Power Analysis**

Power Analyses was conducted with comparison of main outcomes (systolic blood pressure (SBP)) between the control and intervention arms. Based on availability of patients and our capacity, we plan to enroll 500 subjects from four senior centers. Using Intra-class correlation (ICC) of the four centers at 0.0085 level, attrition after the baseline between 20% to 30% level, mean SBP 141 mm Hg and standard deviation (SD) 20, three repeated measurements: baseline, 3 months, and 12 months (Brown and Prescott 2006), the underlying

statistical power of the study comes from two dimensions of observations: the number of unique subjects and the number of repeated measurements within a subject. Based on sample size and power analyses method proposed by Diggle et al. (1994) and Liu et al. (2005) for repeated measures analysis with a type I error of 0.05, type II error of 0.2 (or equivalent to power of 80%), 2.6 and 2.4 average data points for each subject (corresponding to 20% and 30% attrition respectively), and an auto-correlation at 0.2 level, the effective sample size will be 147 and 147 out of the planned 250 and 250 participants in each of the 2 arms (after adjusting for clustering effect), which will enable us to detect an effect size for SBP as small as 0.215 in standard deviation units or 4.29 mm Hg (for 20% attrition), and 0.253 in standard deviation units or 5.06 mm Hg (for 30% attrition).

The seminal work for moderator and mediator effect was from Baron and Kenny (1986). For potential moderators (e.g., age, gender, stroke type and severity, education, country of birth/primary language), we will test power of moderation using the most common measure of effect size  $f^2$  (Aiken & West, 2001), which equals the unique variance explained by the interaction term divided by sum of the error and interaction variances. Cohen (1988) has suggested that  $f^2$  effect sizes of 0.02, 0.15, and 0.35 are termed small, medium, and large, respectively. A more realistic standard for effect sizes with moderators might be 0.005, 0.01, and 0.025 for small, medium, and large, respectively.

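### The primary outcome row in section 9.2 holds two blood pressure measures, other sections point to continuous systolic pressure or to SBP below 120, and no rule says which one decides the trial

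*Combined protocol and SAP*

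**What the plan says.** The places that describe the primary outcome do not agree.

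- Section 9.2, Table 1 (the table to which 9.2.1 refers): "Blood Pressure (change in blood pressure, as well as proportion of patients with BP under 120/80". The change part does not say systolic or diastolic, and neither part has a time point.
- Synopsis, Table 1: blood pressure, with no further definition.
- Synopsis objectives and section 1.1, Objective #2: "control of systolic blood pressure (primary outcome), composite stroke risk, and each individual stroke risk factor (secondary outcomes". Control can mean a lower mean or reaching a threshold.
- Hypothesis under Objective #2: patients in the intervention arm "will achieve 8mm greater reduction in systolic blood pressure reduction and lower stroke risk scores at 1 year". This gives a measure, a size and a time point, but pairs SBP with stroke risk scores.
- Synopsis study design and section 3: "We designate systolic blood pressure as the primary outcome for the purpose of sample size calculations".
- Section 4.2.6: "We will also exclude persons who already meet the primary outcome of SBP <120 mm Hg". This is binary and systolic only, so it is not the 120/80 criterion.
- Section 9.1: "There is no face-to-face contact, and thus, no collection of SBP, the primary endpoint".
- Section 9.3: "Power Analyses was conducted with comparison of main outcomes (systolic blood pressure (SBP)) between the control and intervention arms", with one type I error of 0.05, SD 20 and three repeated measurements including baseline.
- Section 9.5: the same family of regression models is applied to all primary and secondary outcomes, with and without covariates. No measure or model is named as decisive.

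**The concern.** The definitions differ in component (systolic, or systolic and diastolic), in scale (continuous or binary) and in time (1 year, repeated measures, or unstated). A reader of section 9.2 alone would conclude that the trial has two primary measures. A reader of sections 1.1, 9.1 and 9.3 would conclude that it has one.

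Two things are at stake. First, the false-positive rate depends on which reading is applied, and the plan does not fix the reading. Second, the two measures can plausibly disagree at the end of the trial, for example with SBP clearly lowered but no significant difference in the proportion under 120/80. The plan would then give no way to say whether the trial had succeeded, and the choice could be made after the data were seen.

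**Working it through.** **Inputs from section 9.3:** mean SBP 141, SD 20, autocorrelation 0.2, alpha 0.05 (two-sided assumed, since sidedness is not stated), power 80%, effective 147 per arm out of 250, attrition 20% to 30%. **From section 1.1:** hypothesised difference 8 mm Hg at 1 year. **Assumed:** normally distributed SBP. The documents give no diastolic values and no expected proportion, so SBP below 120 stands in for 120/80.

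**1. The plan's own figures.** Detectable difference = (1.960 + 0.842) × 20 × √(2v/147), where v is the variance factor for the mean of m measures with first-order autocorrelation 0.2.
- m = 3: v = 0.4311, giving 4.29 mm Hg (0.215 SD).
- m = 2: v = 0.600, giving 5.06 mm Hg (0.253 SD).

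Both published figures reproduce. They describe SBP averaged over three or two measurements, baseline included. That is neither a change score nor a proportion, so the power analysis fits neither measure in section 9.2.

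**2. False-positive rate under each reading.** With two tests at 0.05 and correlation r, the either-wins rate is 1 − P(|Z1| < 1.96, |Z2| < 1.96).

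| r | Either wins |
|---|---|
| 0 | 9.75% |
| 0.5 | 9.1% |
| 0.8 | 7.8% |
| 0.9 | 7.0% |

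If SBP alone decides, the rate is 5%. If both must win, it is at most 5%.

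**3. A plausible r for change against a threshold.**
- SBP level with its indicator below 120: z = (120 − 141)/20 = −1.05, p = 0.147, r = 0.2299/√(0.147 × 0.853) = 0.65 in absolute value.
- Unadjusted change with 12-month level, autocorrelation 0.2: (1 − 0.2)/√(2 × 0.8) = 0.632.
- Change with the indicator: 0.632 × 0.649 = 0.41, giving an either-wins rate of 9.3%.
- With baseline values below 120 removed, as Table 3 requires, simulation gives r of about 0.47 and a rate of 9.2%.

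Using single-visit level instead of change would give 0.65 and 8.6%, but level is not the measure that section 9.2 lists.

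**4. Can the two measures disagree?** As an illustration on single-visit levels with 147 per arm, an 8 mm Hg shift moves the proportion below 120 from 14.7% to 25.8%. Power is about 93% for continuous SBP and 66% for the proportion. At 4.29 mm Hg the figures are about 45% and 24%. A split result is a practical possibility.

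**5. Detectable difference for a 12-month contrast adjusted for baseline.** This is (1.960 + 0.842) × 20 × √(1 − 0.2²) × √(2/n). For alpha 0.025, replace 1.960 by 2.241.

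| n per arm | alpha 0.05 | alpha 0.025 |
|---|---|---|
| 200 (250 less 20%, no clustering reduction) | 5.5 | 6.0 |
| 175 (250 less 30%, no clustering reduction) | 5.9 | 6.5 |
| 147 | 6.4 | 7.0 |
| 147 less 20% (117.6) | 7.2 | 7.9 |
| 147 less 30% (102.9) | 7.7 | 8.4 |

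Without baseline adjustment, a change score with autocorrelation 0.2 has SD 20 × √1.6 = 25.3. With 147 per arm the detectable difference is then 8.3 mm Hg, above the hypothesised 8.

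**The case against.** The best reply is that the trial plainly has one primary outcome. Section 9.1 calls SBP the primary endpoint without qualification. The objectives attach the primary label to systolic pressure, the hypothesis states 8 mm Hg at 1 year, and only SBP is powered. The section 9.2 row has a singular heading and one entry with a parenthesis. The phrase about sample size in the synopsis and section 3 need not be a restriction. Section 4.2.6 is an eligibility rationale, and section 4.2.2 states the pressure limit in the opposite direction from Table 3 and 4.2.6, so section 4.2 is a weak source for an endpoint definition.

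Much of this stands: the weight of the text favours continuous SBP. It does not close the point. The section that formally defines the primary outcome puts the 120/80 proportion in the primary row, and no other section removes it or ranks it.

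A reader might go further and infer that the trial runs a false-positive rate near 10%. The documents do not support that. No section says that a win on either measure counts, and the 7.0% to 9.75% range comes from assumed correlations. Nor is it right that a split result is uninterpretable whatever reading is taken. If SBP alone decides, the result follows SBP; if both must win, a split is a failure. The gap is that the plan does not say which reading applies.

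**Conclusion.** The concern holds as a conflict over which measure decides the trial, and should be fixed. The formal definition lists two measures, the rest of the plan leans towards one of them, and no alpha split, testing order or both-must-win rule is given. A split result therefore has no pre-stated interpretation.

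Inflation arises only if either measure may count. On that reading, an unadjusted SBP change paired with SBP below 120 gives about 9.2% to 9.3%. This assumes normal SBP and the section 9.3 mean, SD and autocorrelation, and it leaves diastolic pressure out.

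**What to change.** Name one primary: the between-arm difference in SBP change from baseline to 12 months, which is the sponsor's own hypothesis in section 1.1. Test it at two-sided 0.05 in one named model adjusted for baseline SBP, and label other versions as sensitivity analyses. Make the proportion under 120/80 a secondary outcome that cannot establish success on its own, for example tested only if the primary is significant. Align the primary-outcome wording in the synopsis design text and Table 1, section 3, section 4.2.6 and section 9.2 Table 1.

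The cost is wording, with no added patients or visits; the loss of any claim of success on the proportion alone; and a restated detectable difference in section 9.3, because 4.29 and 5.06 mm Hg do not apply to a 12-month contrast. The range of 5.5 to 7.7 mm Hg worked out above stays below 8, with a thin margin at its upper end.

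If the sponsor prefers two primaries, the plan must state an alpha split or a both-must-win rule and add a power calculation for the proportion, which now has none. At 0.025 each, the 12-month detectable difference is about 6.0 to 8.4 mm Hg and may exceed the hypothesised 8.
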